4. DATA ANALYSES

In order to evaluate the effect of the multilevel, multicomponent intervention, we will take a step-by-step approach. First, each intervention effect at each time phase will be estimated separately using linear-mixed effects models. The estimate of intervention effect in each model will be used to test if additional intervention component significantly affects outcome measures. Next, we will develop a grand model including all three intervention effects simultaneously in addition to the models described above.

In this study, patients are nested within providers and providers are nested within clinics. The problem with nested data structures is that they violate the independence assumption of traditional regression models. Thus, we will use multilevel modeling to analyze our data. We will start with the unconditional three-level random intercept models:

$$\text{Level - 1: } Y_{ijk} = \beta_{0jk} + \epsilon_{ijk};$$

$$\text{Level - 2: } Y_{ijk} = \beta_{0k} + u_{jk} + \epsilon_{ijk}$$

$$\text{Level - 3: } Y_{ijk} = \beta_0 + v_k + u_{jk} + \epsilon_{ijk}$$

where Y_{ijk} is the observed outcome for patient i with provider j in clinic k . β_0 is the mean response across all clinic. v_k is the random effect of clinic k , u_{jk} is the random effect of provider j , and ϵ_{ijk} is the residual error. The random effects and residual errors are assumed independent of one another.

Adding predictor variables to the models is straightforward. For example, the level-3 random intercept and slope model with one predictor measured at each level is $Y_{ijk} = \beta_0 + \beta_1 X_{1ijk} + \beta_2 X_{2jk} + \beta_3 k + v_k + u_{jk} + \epsilon_{ijk}$, where $\beta_0 + \beta_1 X_{1ijk} + \beta_2 X_{2jk} + \beta_3 k$ is the fixed effect of the model and $v_k + u_{jk} + \epsilon_{ijk}$ is the random effect of the model. The fixed effect of the model specifies the overall mean relationship between the response and the predictor variables. The random effect of the model specifies how the provider and clinic specific relationships differ from the overall mean relationship. To assess the potential mediator effect, we will use the causal variable and the mediator variable as predictors in the model. To assess the cross-level interaction effects, we will add a product term to the model. For example, the model for a level-1 predictor (e.g. age) cross-level and interact with a level-2 predictor: $Y_{ijk} = \beta_0 + \beta_1 X_{1ijk} + \beta_2 X_{2jk} + \beta_3 (X_{1ijk} \bullet X_{2jk}) + u_{0jk} + u_{1jk} X_{1ijk} + \epsilon_{ijk}$. Since one of the patient-level (level-1) outcome measures is dichotomous (whether the patient adherence to follow-up diagnostic evaluation after a positive result within 9 months or not), we will add another level-1 model for the binary data:

$$\text{Level - 1: } \log [P_{ijk} / (1 - P_{ijk})] = \beta_{0jk} + \beta_1 X_{1jk}.$$

In this study, we will use the restricted maximum likelihood (**REML**) to estimate variances. REML treats the regression coefficients as unknown quantities to be estimated based on sample data and subtracts the needed degree of freedom when computing variance estimates. Since REML only allows for tests of models that differ in their variances, we will calculate the intraclass correlation (**ICC**) to access the variation in response variable across providers and across clinics prior to testing the models. At the end of the analysis, we will use the likelihood ratio test to

compare the nested models. The deviance values ($-2 \log L$) for the two models can be used to decide which model better fits the data:

$$(-2 \log L_{\text{Reduced Model}}) - (-2 \log L_{\text{Full Model}}) = \text{deviance}_{\text{Reduced Model}} - \text{deviance}_{\text{Full Model}}$$

Statistical analyses will be conducted using Statistical Package for the Social Science (SPSS) version 23.0 and the significant level will set at alpha ≤ 0.05 .

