2. STUDY OBJECTIVES, DURATION, AND STUDY SITES

2.1. Study Objectives

Objective 1: *Collect baseline data during the first 6 months before implementing any intervention component.*

Objective 2: *Implement the intervention in three phases: 1) provider education plus community outreach; 2) add provider assessment and feedback + patient reminder; and 3) add a CRC navigator program.*

Objective 3: *Create a grand model to test the overall effectiveness of the multilevel intervention on primary outcomes within and across levels, as well as separate models to assess effectiveness at each phase.*

Objective 4: *Identify potential interaction or mediation effects and assess such effects on primary outcomes.*

Exploratory Objective 5: *Implement a local innovation, IL ColonCARES Program, and assess its feasibility and effectiveness on the follow-up of abnormality.*

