3. STUDY DESIGN AND PROCEDURES

3.1 Study Design

We will use a stepped wedge cluster randomized trial design to assess the effectiveness of our proposed multilevel intervention. Although it will be preferable to use a traditional cluster-randomized trial to test our multicomponent, multilevel intervention, we will need a larger number of clusters, which will be more expensive and infeasible. Also, it is unacceptable for our partner(s) assigned to a control group to not benefit from well-studied evidence-based interventions. Since the stepped wedge design retains some elements of randomization and has the advantage for multiple data collection points over a long period and allows clusters to act as their own control, it is the best alternative to the gold standard.

In the UH3 Implementation phase, we will partner with four FQHCs. We will randomize the four FQHCs to either group 1 or group 2. The biostatistician will conduct the randomization independently from the research team. The difference between the two groups is that group 2 will start the implementation later. We will implement our multilevel intervention in three phases. In phase 1, we will implement the provider education and community outreach component. In phase 2, we will add the mobile patient reminder and the provider assessment and feedback components. In phase 3, we will add the CRC patient navigation component. Figure 1 shows our stepped wedge study design.

Figure 1: Stepped Wedge Study Design.

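### Component tests taken from separate phase models are biased if each model holds one phase indicator and another phase works; the planned grand model should carry these tests

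*Combined protocol and SAP*

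**What the plan says.** Section 4 sets out two stages. First, "each intervention effect at each time phase will be estimated separately using linear-mixed effects models". The use of these estimates is explicit: "The estimate of intervention effect in each model will be used to test if additional intervention component significantly affects outcome measures". Second, "we will develop a grand model including all three intervention effects simultaneously in addition to the models described above".

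Objective 3 in section 2.1 divides the work in the same way. The grand model is for overall effectiveness, "as well as separate models to assess effectiveness at each phase".

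The phases are cumulative. Section 3.1 states "In phase 2, we will add the mobile patient reminder and the provider assessment and feedback components", and phase 3 then adds navigation to what is already running. On allocation it says "We will randomize the four FQHCs to either group 1 or group 2", and the only difference between the groups is that "group 2 will start the implementation later".

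The text does not say how a phase is coded in a separate model, which quarters enter it, whether calendar time is included, or which model decides if the separate and grand models disagree.

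**The concern.** A plan that sets effects estimated separately against a model holding all three at once is most naturally read as one phase effect per separate model. Because the phases accumulate, a model holding only a phase 2 indicator compares phase 2 and later quarters with a mixture of baseline and phase 1 quarters. Its coefficient is not the increment over phase 1, because part of phase 1's effect leaks into it. Carry-over of screening status is not needed for this, and adding quarter terms changes the leak without removing it.

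The per-phase part of Objective 3 is at stake. Reminders with feedback, or navigation, could appear effective or harmful because of the roll-out schedule and the coding, and not because of what they do.

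**Working it through.** The plan gives no power or effect-size figure to reproduce. The check asks what each model would estimate, without noise, under a known truth.

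**Inputs from the document**
- Four FQHCs in two groups, group 2 later (section 3.1).
- Four years (section 2.2) with quarterly data (section 3.5), taken as 16 quarters.
- Six months of baseline (section 2.1), that is 2 quarters. Section 3.5 gives three months for collecting it, so 1 quarter was also tried.

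**Assumptions**
- Lag g of 2 to 4 quarters, and phases 1 and 2 of L1 and L2 = 2 to 4 quarters each, with phase 3 to the end: 3 × 3 × 3 = 27 schedules. The design figure is not shown in the text available and may settle these values.
- Two FQHCs per group, equally weighted, with an intercept for each FQHC.
- Truth +5, 0, 0 points for phases 1, 2, 3, with no trend.

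**1. One cumulative indicator, all quarters, no quarter terms.** Within a group, the on-minus-off difference is 5 × (baseline quarters) / (all off quarters). Groups are combined with weights n_on × n_off / 16. Example: g = L1 = L2 = 3.
- Phase 2 or later, group 1: 5 × 2/5 = 2.00, weight 11 × 5/16 = 3.4375.
- Phase 2 or later, group 2: 5 × 5/8 = 3.125, weight 8 × 8/16 = 4.
- Estimate: (3.4375 × 2.00 + 4 × 3.125) / 7.4375 = 2.61. Truth 0.
- Phase 3: (4 × 1.25 + 3.4375 × 2.273) / 7.4375 = 1.72. Truth 0.

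Over the 27 schedules, phase 2 is +2.10 to +3.21 and phase 3 is +1.30 to +2.33. The phase 1 model returns 5.00 in all 27. With a one-quarter baseline, lag 2 and four-quarter phases, phase 2 is (3.4375 × 1.00 + 3.9375 × 2.143) / 7.375 = +1.61.

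**2. The same with quarter terms.** Only the difference between groups within a quarter now informs the estimate. The true difference is 5 in the g quarters when group 1 has started and group 2 has not. The phase 2 indicator differs between groups in g quarters, of which k = max(0, g - L1) coincide with those. The estimate is 5 × [k/g - (g - k)/(16 - g)].
- g = 4, L1 = 4: 5 × (0 - 4/12) = -1.67.
- g = 4, L1 = 2: 5 × (2/4 - 2/12) = +1.67.
- g = 4, L1 = 3: 5 × (1/4 - 3/12) = 0. This happens in 3 of the 27.

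For phase 3, k = 0 throughout, so the estimate is -5g/(16 - g): -0.71, -1.15 or -1.67 for g = 2, 3, 4.

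**3. If later phases work.** With truth +5, +5, +5 in the step 1 example, the phase 1 model gives (1.75 × 165/14 + 3.4375 × 120/11) / 5.1875 = 11.20, where phase 1 itself contributes 5.

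**4. Coding each phase against all other quarters, with quarter terms.** In the same example with truth +5, 0, 0, phase 1 falls to 15/6 = 2.5 and null phase 2 is 0. Over the 27 schedules null phase 2 is 0 in 18.

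**5. Adjacent phases only.** Without quarter terms this returns 5, 0, 0 in all 27. Now assume instead a background rise of 0.5 points per quarter and no intervention effect. Phase 2 against phase 1 then gives 0.5 × (L1 + L2)/2, which is +1.0 to +2.0. Over all three comparisons the range is +1.0 to +2.8. With quarter terms, the phase 2 increment needs a quarter in which both groups are in phase 1 or both in phase 2, hence g < L1 or g < L2. It is not estimable when g is at least as long as both phases: 1 + 4 + 9 = 14 of the 27 (for g = 2, 3, 4).

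**6. Grand model, step-coded, with quarter terms.** All three increments are estimable in all 27 schedules and return 5, 0, 0.

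**7. False rejection.** A rough mixed-model simulation used 60 runs, 35 clinics, lag 2, four-quarter phases, and assumed SDs of 5 (clinic) and 4 (clinic-quarter residual) points. Single-indicator models without time terms rejected null phases 2 and 3 in 100% and 88% of runs; with quarter effects, in 10% and 13%. The grand model rejected in 3% to 7%.

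**The case against.** The strongest reply is that the one-indicator reading is inferred. The plan gives neither coding nor comparison period, and testing an additional component could equally mean comparing each phase with the one before, which has no omitted-phase bias. The equations in section 4 are unconditional models and worked examples with no phase term at all, so the absence of a quarter term in them does not show what will be fitted. The unbiased grand model is already planned in the same paragraph.

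Much of this stands. The adjacent-phase reading is not excluded, and the sizes rest on an assumed schedule. That the grand model returns 5, 0, 0 is also no surprise, since it contains the assumed truth; this shows that it is estimable and free of the leak, and says nothing about its precision with four FQHCs.

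The reply does not dispose of the point, for two reasons. Section 4 and Objective 3 both give the per-phase question to the separate models, and nothing gives the grand model precedence. The adjacent-phase reading has its own trouble, as step 5 shows.

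A reader might infer that every test in the plan is biased, or that a phase that does nothing must receive a non-zero estimate. The documents do not support either. The grand-model tests are free of this bias. The cumulative phase 1 test is unbiased when later phases do nothing. Some schedules and codings give exactly zero for a null phase 2. If no phase works, every model gives zero in the absence of a trend.

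**Conclusion.** The concern holds conditionally. If each separate model holds one phase indicator fitted to all quarters, which is the natural but not the only reading, a component's test is biased whenever another phase has an effect. With an assumed +5 points for phase 1 alone and cumulative coding, the leak into null later phases is about 1.3 to 3.2 points without quarter terms. With quarter terms it is at most about 1.7 points in either direction. Sign and size depend on lag, phase lengths and coding, all assumed here, and scale with the assumed 5 points.

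If the separate models compare adjacent phases, the omitted-phase bias disappears. What remains is a choice between counting background trend as effect and, in about half of these schedules, having no estimable phase 2 increment. Under neither reading are the separate models a sound basis for the component tests, while the plan already contains a model that is.

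**What to change.** State in section 4, and align Objective 3, that every added-phase test comes from the grand model. Code the phases in steps (phase 1 or later, phase 2 or later, phase 3), so that each coefficient is the increment over the phase before, and include an effect for each calendar quarter. The quarter effects are needed because a grand model without them would still count a background trend as effect. Report the separate single-phase models as descriptive only, with their coding and comparison quarters stated.

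The cost is a change of wording, with no new data and no change to the design. The quarter effects may widen the intervals somewhat.

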2.2. Study Duration and Study Sites

The ACCSIS – Chicago UH3 Implementation Phase will last for four years (November 2019 to October 2023). In the UH3 Implementation Phase, we will have 4 clusters of clinics from four different FQHCs. Each cluster will have 5 to 12 clinics and a total of 20 to 35 primary care providers (internist, family practice physician, nurse practitioners, and physician assistants). Table 1 summarizes the characteristics of our FQHC partners. Together, our

Table 1: Characteristic of Partner Health Care Systems

	Total Patients	% of Racial Minority	% at or below 200% poverty	% of Uninsured	CRC Screening Rate	Adjusted Quartile Ranking on CRC Screening ¹	No. of Clinics ²	No. of Providers
PCC Community Wellness Center	48,357	92.2%	93.1%	9.3%	30.0%	Quartile 4	11	60
Aunt Martha's Youth Service Center, Inc.	51,343	80.9%	96.2%	16.5%	32.9%	Quartile 3	12	21
Lawndale Christian Health Center	51,235	96.9%	97.6%	30.2%	35.0%	Quartile 2	5	35
Near North Health Service Corporation	37,102	94.6%	97.3%	35.1%	31.0%	Quartile 3	7	20

1. Adjusted Quartile Ranking provides a health center's adjusted quartile ranking compared to health centers nationally for each of the clinical performance measures. Clinical performance for each measure is ranked from quartile 1 (highest 25% of reporting health center) to quartile 4 (lowest 25% of reporting health centers).

2. Reported by partner health care system.

partner FQHCs served 188,037 patients in 2016, and at least 10% of these patients were ≥ 50 years old. It is important to point out that three of our partners' CRC screening rates were in the lower third and fourth quartiles compared to other FQHCs in the nation, indicating room for improvement. We will continue to monitor their ranking throughout the study.

[figure not shown]

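### Section 4 prespecifies no calendar-time term, so the grand model as described would credit most of a sustained background trend to the intervention phases

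*Combined protocol and SAP*

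**What the plan says.** Section 3.1 chooses a stepped-wedge cluster randomised design. Four FQHCs are randomised to group 1 or group 2, and the only difference is that group 2 starts later. All FQHCs take up the three phases cumulatively and in the same order. The implementation period "will last for four years (November 2019 to October 2023"; Section 3.5 and its Table 2 call for outcome data every quarter.

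Section 4 is the whole analysis plan. Its first step is: "First, each intervention effect at each time phase will be estimated separately using linear-mixed effects models". Its second is: "Next, we will develop a grand model including all three intervention effects simultaneously in addition to the models described above". Section 2.1, Objective 3, gives that second model its purpose: "Create a grand model to test the overall effectiveness of the multilevel intervention on primary outcomes within and across levels".

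The grand model is never written as an equation. The printed equations are starting or example models. Their outcome "is the observed outcome for patient i with provider j in clinic k" carries no time index, and their random effects are for provider and clinic. Section 4 adds that "Adding predictor variables to the models is straightforward", but the only predictor it names is age, as an example. For the dichotomous follow-up outcome, "we will add another level-1 model for the binary data"; that logit equation has no time term either.

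**The concern.** In a stepped-wedge trial, later quarters contain more intervention by construction. The randomised information lies in the comparison of the two groups while they are in different phases. The change within an FQHC from baseline to phase 3 is a before-after comparison, and only a time term separates it from whatever else changed over those years.

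If the grand model is fitted with phase indicators and no time term, a sustained rise in screening that would have happened anyway is reported largely as intervention effect, and a sustained fall hides a real effect. The protocol itself shows that this outcome can drift: Section 1.1 reports national up-to-date screening rising from 54% in 2002 to 65% in 2010. At stake is the main effectiveness conclusion. If the time term is left open until the data are seen, that conclusion can turn on an analyst's choice.

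**Working it through.** The plan gives no power, sample size or effect figure to reproduce, so the check computes the expected bias directly: set every phase effect to zero, add a drift, and see what the model reports.

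**Inputs from the documents.** 16 quarters (four years, Section 2.2). Four FQHCs with 11, 12, 5 and 7 clinics, 35 in all, and screening rates of 30–35% (table in Section 2.2). Baseline of two quarters (synopsis and Objective 1) or one quarter (Section 3.5); these conflict, so both were run. National trend (65 − 54)/8 = 1.375 points a year = 0.344 a quarter, or 15 × 0.344 = 5.16 points from first to last quarter.

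**Assumed**, because the schedule figure is not shown and no variances are given: lag between groups, phase lengths, a 2:2 split, clinic SD of 5 points, 10% of patients eligible, screening at 32%.

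**Worked example.** Two-quarter baseline, four-quarter lag, phases 1 and 2 of four quarters each, equal-sized clusters. Take the outcome to be the quarter number itself (pure drift, no effect).

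| | Baseline | Phase 1 | Phase 2 | Phase 3 |
|---|---|---|---|---|
| Group 1 quarters (mean) | 1–2 (1.5) | 3–6 (4.5) | 7–10 (8.5) | 11–16 (13.5) |
| Group 2 quarters (mean) | 1–6 (3.5) | 7–10 (8.5) | 11–14 (12.5) | 15–16 (15.5) |
| Difference, group 2 − group 1 | 2 | 4 | 4 | 2 |
| Weight n1·n2/(n1+n2) | 1.5 | 2 | 2 | 1.5 |

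- Group contrast = (1.5×2 + 2×4 + 2×4 + 1.5×2)/7 = 22/7 = 3.143.
- Adjusted baseline mean = [2×1.5 + 6×(3.5 − 3.143)]/8 = 0.643.
- Adjusted phase 3 mean = [6×13.5 + 2×(15.5 − 3.143)]/8 = 13.214.
- Spurious phase 3 effect = 13.214 − 0.643 = 12.571 quarters of drift; 12.571/15 = 84%.
- At 0.344 points a quarter: 12.571 × 0.344 = 4.3 points with no true effect.

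**Across schedules.** Generalised least squares on clinic-quarter means, with fixed FQHC effects and a random clinic intercept, over 60 schedules (baseline 1 or 2 quarters, lag 2 or 4, phases 1 and 2 of 2–5) and six 2:2 allocations:

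- Linear drift: 67–89% goes into phase 3 versus baseline. That is 3.5–4.6 points at 1.375 points a year, and 1.3–1.7 at 0.5 points a year (15 × 0.125 = 1.875 points in total).
- Wider grid of 230 layouts (lags and phases of 1–6 quarters, cluster intercepts): 60–96%, median 75%, all above half. With no clinic variance at all, the minimum falls to about 49%.
- Sustained step starting in quarters 4–12: median 103% absorbed (range 52–117%). Steps near either end of the study are absorbed much less.
- Temporary dip of 1–6 quarters: a median of about a quarter of its depth, negative in about 60% of placements and positive in the rest.

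**With fixed quarter effects.** A common trend lies wholly within those terms. The spurious effect is zero to rounding in every layout, and all three phase effects remain estimable.

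**Precision.** In the worked example the groups differ in phase in three windows of four quarters and share a phase in the other four quarters. The total effect is three times the mean group difference in the shared quarters minus the sum of the three window means. With two clusters per group and independent residuals of SD σ, the group difference in one quarter has variance σ². The variance of the total is therefore 9σ²/4 + 3σ²/4 = 3σ², giving SE 1.73σ against 0.38σ without quarter effects: 4.6 times. Over the 60 schedules the SE rises from 0.22–0.31 to 0.68–1.18 points, or 2.8–4.6 times.

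**The case against.** The strongest reply is that the plan is silent rather than wrong. The grand model is never printed, the equations shown are starting points and examples, and predictors may be added, so a competent analyst could include time. That stands as far as it goes: what is proved is that no time term is prespecified, and the bias is conditional on none being added. But a prespecified effectiveness test should not depend on that addition, and the one description given lists only the intervention effects.

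Second, the separate phase models might compare group 1 with group 2 in the same calendar window, which would remove a common trend. That is possible, but the text does not say so. Such models have a contrast only while the groups are in different phases (in the 60 schedules they share a phase in 4–10 of 16 quarters), and they do not rescue the grand model.

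Third, the share depends on the assumed schedule, the point values borrow a national trend from an earlier decade, and the illustration covers one of the eight measures in Section 3.5, Table 2. All of this is true. The finding that most of a sustained drift is absorbed survives the wider grid; an exact percentage does not.

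Fourth, quarter effects are not a full cure. They assume one trend for all FQHCs. With two FQHCs trending at +0.5 and two at −0.5 points a year around the mean, the residual absolute bias has a median of 0.20 points over 2,160 cases. In the third where trend direction coincides with group (720 cases), the median is 2.0 and the maximum 4.8; in the rest it is 0.16 and 0.46. Adjustment does worse than none in 3% of cases at a mean trend of 1.375 points a year, and in 23% at 0.5. This supports a stated assumption and a sensitivity analysis, not omission of time.

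Finally, a linear time term also removes a linear drift, at a lower cost (SE up 1.7–3.4 times against 3.9–4.6 in five layouts). It would not deal with steps or dips, so categorical quarters are the safer primary choice.

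**Conclusion.** The concern holds and needs correction before analysis. Section 4 commits to no calendar-time term. The grand model, fitted as described, would attribute most of a sustained common trend to the phases: 67–89% over the 60 schedules and 60–96% over the wider grid. At 1.375 points a year, the spurious 3.5–4.6 points are more than ten times the unadjusted standard error (3.46/0.31 ≈ 11), so the error would look like a precise result.

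This rests on the assumed schedule, a trend shared by all FQHCs, and some variation between clinics. The actual drift at these sites is unknown. A temporary shock would bias the result less and in either direction.

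**What to change.** In Section 4, index the outcome by quarter and write out the grand model, fitted to all quarters of both groups together. For example:

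Y = β0 + FQHC (fixed) + quarter (fixed, categorical) + phase 1, 2 and 3 indicators + clinic, provider and patient random effects + error.

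- Put the same quarter effects in the logit model and in any separate phase models that are kept.
- State that the adjustment assumes a secular trend common to all FQHCs, and name a sensitivity analysis for FQHC-by-quarter variation.
- The FQHC term and the recurrence of clinics, providers and patients across quarters are not needed to remove a common trend. They belong in the same equation because FQHC is the unit of randomisation and quarterly records repeat.
- Confirm that group 2's waiting quarters are collected quarterly. Table 2 says every quarter, but the text ties quarterly collection to the start of implementation, and the adjusted comparison depends on those quarters.

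If that is confirmed, the change is wording only. The real cost is precision, because the effect then rests on the stagger between two groups formed from four FQHCs. Beyond the 2.8–4.6-fold rise above, an assumed FQHC-by-quarter SD of 1 point takes the SE from 0.39–0.54 to 1.21–2.10 points. If patient errors correlate 0.8 between adjacent quarters and this is modelled, the SE goes from 0.30–0.32 to 0.53–0.96. The wider interval is the one this design can support.
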